2.2.2 Secondary endpoints

The secondary efficacy endpoints include:

- Progression-free survival (PFS), defined as the time (days) from date of randomization to date of first observed disease progression (investigator's radiological or clinical assessment) or death due to any cause, if death occurs before progression is documented. Patients without tumor progression or death at the time of analysis will be censored at their last date of tumor assessment.
- Time to Deterioration is defined as the time between the date of randomization and the first time the patient has a WHO \geq 2 during treatment.
- Disease control rate (DCR), defined as the rate of patients, whose best response was not progressive disease (i.e., CR, PR or SD), to all randomized patients in the treatment group-Objective response rate (OOR), defined as the rate of patients with CR or PR, to all randomized patients in the treatment group. Patients prematurely discontinuing without an assessment will be considered non-responders for the analysis.

- Safety will be evaluated by clinical and biological means and scored on the NCI-CTCAE version 5.0 scale, performed at each visit (every 2 weeks).
- -Quality of life will be evaluated, based on the EORTC QLQ-C30 questionnaire (appendix 2).

[figure not shown]
3. Experimental plan

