- d: CT scan of the abdomen, pelvis and chest or hepatic MRI and CT scan of the pelvis and chest without injection; RECIST criteria version 1.1
- e: Paraffin-embedded human solid tissue blocks will be sent off at room temperature at the end of the inclusions
- 1: A 12-lead ECG will be performed at the end of every other cycle (8 weeks, if there's no postponed treatment)
- 2: D1 and D15 of the first two cycles for Bras B (Stivarga®) and D1 only at the other cycles
- 3: Tumor markers CEA and CA 19-9 at every cycle
- 4: If the last clinical and laboratory evaluations > 7 days
- 5: if not done at the EOT visit
- 6: If the last radiological tumor assessment > 1 month
- 7: C1-C2 D8 (arm A): vital signs without height, weight and BSA
- 8: As applicable
- 9: A treatment diary will be handed over to patient on cycle 1 day 1
- 10: EORTC QLQ-C30 questionnaires will be completed by the patient on Day 1 of Cycle 1 then at each evaluation (= 8 weeks) for both treatments

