5.3 Treatment period

REGIRI or Regorafenib:

After all screening assessments have been completed and the patient's eligibility has been confirmed and documented, the patient will be randomized.

The following assessments should be performed on the first day and day 15 of each cycle (REGIRI) or cycle (Regorafenib) except C1D1 prior to receiving study treatment (+/- 3 days):

- Physical examination with weight, body surface area (if the patient's body weight changes by more than 10 % then BSA will be recalculated for Regorafenib and it will be recalculated for any change of weight for Irinotecan) and vital signs (heart rate, blood pressure)
- ECOG performance status :
- Adverse events documentation (including Start/Stop dates, seriousness, CTC notation and grading, relationship to study drug, outcome and action taken) using CTCAE V5.0
- Concomitant medications (including start/stop dates, dose, indication)
- 12-lead ECG. It will be performed every other cycle (8 weeks if there's no postponed treatment) for both arms
- The following laboratory evaluations are not required at Day 1 of Cycle 1 if these
 were completed within 7 days of starting study drug treatment. Otherwise, these
 laboratory evaluations are required on Day 1 and 15 of each cycle:
 - → CBC with differential should be performed: RBC, hemoglobin, hematocrit, platelet count and WBC. WBC must include differential neutrophil, lymphocyte, monocyte, basophil and eosinophil counts
 - → Coagulation panel: Prothrombin time (PT) or the International Ratio of PT (PT-INR) and Partial Thromboplastin Time (PTT)
 - → Electrolyte panel: sodium, potassium, chloride, calcium
 - → Chemistry panel : albumin, lipase, phosphate, glucose, serum creatinine, clearance calculated according CKD-EPI (appendix 7)
 - → Hepatic panel: Aspartate Amino-Transferase (AST), Alanine Amino-Transferase (ALT), bilirubin (total and direct), GGT, alkaline phosphatase, Lactic Dehydrogenase (LDH)

- → Thyroid function test (TSH, free T3, free T4, on day 1 of each cycle for both arms)
- Tumor markers CEA (Carcino-Embryogenic Antigen), CA 19-9 (carbohydrate Antigen 19-9) every cycle for both treatments
- A β-HCG dosage for women of childbearing potential. Post-menopausal women with no menses for at least 1 year or surgically sterilized women will not be required to undergo a pregnancy test (on day 1 of each cycle for both arms).
- Urine analysis by urinary dipstick. If results of protein ≥ 3+, then quantification

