 of proteinuria on a 24-hour urine collection must be done.
- EORTC QLQ-C30 (appendix 2) questionnaires will be completed by the patient on Day 1 of Cycle 1 (baseline) then on the first day of every other cycle (every 8 weeks)
- Drug dispensing
- Drug accountability (pharmacy). To have complete control over the distribution and use of the study drug, the drug accountability must be performed on Day 1 for arm A (REGIRI) and B (Regorafenib) of each cycle

Provide patient's diary on C1D1. It will allow to patient to write down his oral intakes and blood pressure values

The blood pressure must be monitored weekly for the first six weeks of study treatment. The blood pressure will be recorded by the patient and entered onto his treatment diary. In the latter case, the patient should be instructed to contact the physician in the event of systolic \geq 150 mm Hg and / or diastolic \geq 100 mm Hg. The physician should confirm the reading before recording it into the e-CRF. Blood pressure measurements will be performed in patients sitting for 5 minutes prior to the evaluation. The patient should be instructed to take their blood pressure in the morning and repeat two more times for accuracy.

The following assessments should be performed on day 8 of cycle 1 and 2:

REGIRI (arm A)

- Vital signs (Heart rate and blood pressure)
- these laboratory evaluations are required: Aspartate Amino-Transferase (AST), Alanine Amino-Transferase (ALT), bilirubin (total and direct)

Stivarga® (Regorafenib) (arm B):

• Phone call by a treatment nurse for knowing if there are any adverse events and blood pressure value (current state of the art)

The following assessments should be performed on day 15 of cycle 1 and 2:

REGIRI (arm A)

- Physical examination with weight and vital signs (heart rate, blood pressure)
- ECOG performance status
- Concomitant medications (including start/stop dates, dose, indication)
- Adverse events documentation (including Start/Stop dates, seriousness, CTC notation and grading, relationship to study drug, outcome and action taken) using CTCAE V5.0
- A CBC with differential should be performed: RBC, hemoglobin, hematocrit, platelet count and WBC. WBC must include differential neutrophil, lymphocyte, monocyte, basophil and eosinophil counts
- Coagulation panel: Prothrombin time (PT) or the International Ratio of PT (PT-INR) and Partial Thromboplastin Time (PTT)
- Electrolyte panel: sodium, potassium, chloride, calcium

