- Chemistry panel: albumin, lipase, phosphate, glucose, serum creatinine, clearance calculated according CKD-EPI (appendix 7)
- Hepatic panel: Aspartate Amino-Transferase (AST), Alanine Amino-Transferase (ALT), bilirubin (total and direct), GGT, alkaline phosphatase, Lactic Dehydrogenase (LDH)
- Urine analysis by urinary dipstick. If results of protein ≥ 3+, then quantification of proteinuria on a 24-hour urine collection must be done.
- Drug accountability (pharmacy)
 Verify patient's diary. It will allow to patient to write down his oral intakes and blood pressure values

The following assessments should be performed on day 15 of cycle 1 and 2:

Stivarga® (Regorafenib - arm B):

• these laboratory evaluations are required: Aspartate Amino-Transferase (AST), Alanine Amino-Transferase (ALT), bilirubin (total and direct)

The following assessments should be performed on day 22 of cycle 1 and 2:

REGIRI (arm A):

- Phone call by a treatment nurse for knowing if there are any adverse events and blood pressure value (current state of the art)
- These laboratory evaluations are required: Aspartate Amino-Transferase (AST),
 Alanine Amino-Transferase (ALT), bilirubin (total and direct)

The following assessments should be performed at each evaluation i.e (every 8 weeks):

REGIRI or Regorafenib:

 Tumor markers CEA (Carcino-Embryogenic Antigen), CA 19.9 (Carbohydrate Antigen 19-9)

 Radiological tumor assessment using the RECIST criteria, version 1.1 (see Appendix 5) must be performed. (CT scan of the abdomen, pelvis and chest or hepatic MRI and CT scan of the pelvis and chest without injection)

A PET scan is not acceptable for radiological evaluation. Throughout the study, the identical lesions to those identified and measured at baseline must be evaluated using the same technique, and preferably by the same radiologist. Copies of all CT scans performed for tumor assessment in non-progressive enrolled patients will be stored on CDs at the site

 EORTC QLQ-C30 (appendix 2) questionnaires will be completed by the patient at each evaluation i.e 8 weeks

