5.4 End of treatment Visit

When a patient is taken off treatment, the following assessments should be performed within 14 days after study treatment has stopped provided the last clinical and laboratory

evaluations > 7 days.

- Physical examination with weight, BSA and vital signs (heart rate, blood pressure)
- ECOG performance status
- Adverse events documentation (including Start/Stop dates, seriousness, CTC notation and grading, relationship to study drug, outcome and action taken) using CTCAE V5.0
- Concomitant medications
- 12 lead ECG

- A CBC with differential should be performed: RBC, hemoglobin, hematocrit, platelet count and WBC. WBC must include differential neutrophil, lymphocyte, monocyte, basophil and eosinophil counts
- Coagulation panel: Prothrombin time (PT) or the International Ratio of PT (PT-INR) and Partial Thromboplastin Time (PTT)
- Electrolyte panel: sodium, potassium, chloride and calcium
- Chemistry panel: albumin, lipase, phosphate, glucose, serum, creatinine, clearance calculated according CKD-EPI (appendix 7)
- Liver function test panel: Aspartate Amino-Transferase (AST), Alanine Amino-Transferase (ALT), bilirubin (total and direct), GGT, alkaline phosphatase, Lactic Dehydrogenase (LDH)
- Thyroid function test: TSH, free T3, and free T4
- Tumor markers: CEA (Carcino-Embryogenic Antigen), CA 19.9 (Carbohydrate Antigen 19-9)
- Urine analysis by urinary dipstick. If results of protein ≥ 3, then quantification
 of proteinuria on a 24-hour urine collection must be done
- A radiological tumor assessment using the RECIST criteria, version 1.1 (see Appendix 5) must be performed if the last radiological assessment > 1 months. (CT scan of the abdomen, pelvis and chest or hepatic MRI and CT scan of the pelvis and chest without injection)
- Drug accountability (pharmacy)

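### Control-arm ECOG days conflict between the visit table and the lead-in to section 5.3, so Time to Deterioration may be dated on unequal schedules, with a modest bias against REGIRI

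*Combined protocol and SAP*

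**What the plan says.** Time to Deterioration is a secondary objective (2.1.2). Section 2.2.2 dates it from randomization: "Time to Deterioration is defined as the time between the date of randomization and the first time the patient has a WHO" score of 2 or more while on treatment. The schedule lists ECOG and no separate WHO assessment, so I take the ECOG visits as its source.

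On-treatment ECOG is described in three places:

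- **Visit table, 5.1.** ECOG is marked on day 1 of each cycle for regorafenib, and on day 1 and day 15 for REGIRI. The regorafenib arm has no day-15 column. Its day-15 liver tests appear only through a footnote: "D1 and D15 of the first two cycles for Bras B (Stivarga®) and D1 only at the other cycles".
- **Lead-in to 5.3.** "The following assessments should be performed on the first day and day 15 of each cycle (REGIRI) or cycle (Regorafenib) except C1D1". The list beneath includes ECOG with no restriction by arm or day.
- **Day-15 lists in 5.3.** Both are headed "The following assessments should be performed on day 15 of cycle 1 and 2". The REGIRI list includes ECOG. The arm B list contains only liver tests: "these laboratory evaluations are required: Aspartate Amino-Transferase (AST), Alanine Amino-Transferase (ALT), bilirubin (total and direct").

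Section 2.2.2 also describes safety evaluation as "performed at each visit (every 2 weeks"), without separating the arms.

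For PFS, 2.2.2 gives a censoring rule: "Patients without tumor progression or death at the time of analysis will be censored at their last date of tumor assessment". Time to Deterioration has none, and 9.3 names no test for it; 9.3 leaves the SAP to be written before database lock. Section 5.4 includes an ECOG at the end-of-treatment visit, whose assessments "should be performed within 14 days after study treatment has stopped provided the last clinical and laboratory" evaluations are more than 7 days old. Whether that value counts as during treatment is not stated.

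**The concern.** An event that can only be recorded at a visit is dated at the first visit after it happens. If one arm is examined every 2 weeks and the other every 4 weeks, the second arm looks better with identical true deterioration. Under the table that advantage goes to regorafenib. Under the lead-in there is no such difference. Sites reading different parts of the protocol could therefore produce different results for the same endpoint, and the protocol gives no analysis rule for unequal intervals.

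**Working it through.** The documents give no figure for this endpoint, so there is none to reproduce.

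**1. The passages side by side**

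| Place | Regorafenib | REGIRI |
|---|---|---|
| 5.1 table | Day 1 | Days 1 and 15 |
| 5.3 lead-in | Days 1 and 15 | Days 1 and 15 |
| 5.3 day-15 lists, cycles 1 and 2 | No ECOG | ECOG |

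In the list under the lead-in, thyroid and β-HCG tests are limited to day 1 for both arms, while ECOG is not. Read literally, it requires day-15 ECOG in both arms and contradicts the other two places.

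**2. Detection delay under the table**

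For visits every w days and onset evenly spread between visits, the mean delay is w/2. REGIRI: 14/2 = 7 days. Regorafenib: 28/2 = 14 days. The difference is 7 days.

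**3. Apparent hazard ratio with no true difference**

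Inputs: 39 per arm (9.1); intervals of 14 and 28 days (5.1). The documents give no deterioration rates, so exponential times with medians of 2 to 6 months are assumed. Each onset is moved to the next visit; 1000 runs per row.

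| Assumed median, months | HR, REGIRI vs regorafenib | Two-sided rejections | Against REGIRI | For REGIRI (difference) | HR, 14 days in both arms |
|---|---|---|---|---|---|
| 2 | 1.13 | 9.6% | 9.0% | 0.6% | 1.00 |
| 3 | 1.08 | 7.9% | 6.4% | 1.5% | 0.99 |
| 4 | 1.07 | 5.7% | 4.4% | 1.3% | 0.99 |
| 6 | 1.03 | 5.6% | 3.9% | 1.7% | 0.99 |

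With 14 days in both arms, rejections were 4.8 to 6.8%. The simulation standard error of a 5% rate is √(0.05 × 0.95 / 1000) = 0.7 points.

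A fuller model added treatment stopping (assumed medians of 2 to 4 months), a 7-month OS median in both arms, 64 months of accrual with cut-off at 69 months, and censoring at the last ECOG. It gave HR 1.06 to 1.16 with 4.5 to 8.1% rejections under the table, and 0.99 to 1.02 with 14 days in both arms. A further null run, censored at last ECOG with a log-rank-based hazard ratio, gave about 1.07 to 1.21 under the table and 1.00 to 1.03 with equal schedules. Together the range is about 1.03 to 1.2.

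**4. Against sampling noise**

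The SD of the log hazard ratio in the fuller model was 0.32 to 0.59. The bias is ln(1.03) = 0.03 to ln(1.2) = 0.18. Pairing the largest bias with the smallest SD gives 0.18/0.32, or about 0.6 of one SD.

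**5. Restricting to Day-1 ECOG**

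In the fuller model this gave HR 0.99 to 1.02 and 4.5 to 6.2% rejections. If 15 to 30% of REGIRI courses slip by 7 days (an assumption), it gave 0.91 to 0.96, now in favour of REGIRI. Two-weekly ECOG in both arms gave 0.98 to 1.01 under the same slippage. Delays in arm B were not modelled.

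**6. Timing**

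Inclusion began in September 2019 and runs 64 months. Version 6.0 is dated 09/11/2023, about 50 months in: 50/64 = 78%.

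**The case against.** The strongest reply is that this is a schedule-editing slip and not a defect of the endpoint. The mismatch covers the whole arm B day-15 visit, including examination and blood tests. The lead-in is awkwardly worded and may be two headings badly merged; if it truly applied to arm B, the separate arm B liver list would be largely redundant. The two-weekly phrase in 2.2.2 concerns safety scoring, not ECOG.

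Much of this stands: the text leans toward the table. The missing table mark is weak evidence alone, because the table has no arm B day-15 column, but the arm B list points the same way. This does not remove the problem. If the table is the likelier reading, the unequal schedule is the likelier practice, and that is the one that biases the comparison.

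It is also fair that the missing test and censoring rule are details the SAP can supply and would not make a point alone. The caution about Day-1-only analysis also stands: section 6.3 allows irinotecan to be delayed up to two weeks for toxicity at day 15, which can move Day 1 later in REGIRI. The restricted analysis should therefore be reported beside the all-assessments one and not replace it.

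**Conclusion.** The documents contradict themselves on control-arm ECOG days, and a named secondary endpoint depends on them. If the table is followed, the expected result is a hazard ratio of about 1.03 to 1.2 against REGIRI with no true difference. This rests on assumed medians of 2 to 6 months, deterioration that persists once it occurs, and, in the models with stopping, assumed stopping rates. If every site follows the lead-in, there is no schedule bias.

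A reader might infer more than this:

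- **A risk of falsely claiming benefit.** In the simulation tabulated above, false rejections favouring REGIRI were 0.6 to 1.7%, below the nominal 2.5%. The excess is against REGIRI.
- **Hazard ratios up to 1.24 with 11% false positives.** These need censoring at treatment stop, which no passage states.
- **Hazard ratios of 1.30 to 1.48.** These need many episodes of WHO 2 or more to last under about 4 weeks (exponential lengths with mean 4 to 8 weeks). The documents say nothing on episode length.
- **Doubt about the primary result.** Overall survival does not depend on ECOG visits.

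This is a modest point on a secondary endpoint, worth correcting because the correction is cheap.

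**What to change.** **Protocol.** Reconcile the 5.1 table and the day-15 lists in 5.3 with the 5.3 lead-in, so that ECOG is scheduled on the same days in both arms for remaining patients. This needs a clarification under 12.6; if day 15 is kept in both arms, arm B gains an ECOG. It cannot equalise visits already made and may leave two schedules within arm B, so the analysis rule is needed as well.

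**SAP.** Prespecify a Time to Deterioration comparison restricted to Day-1-of-cycle ECOG, reported beside the all-assessments analysis. Report the actual interval between ECOGs by arm. State one censoring rule, such as the last included ECOG, and whether the end-of-treatment ECOG counts, identically in both arms. If it counts but is waived because evaluations were made within 7 days, let those evaluations stand in both arms. Name the test.

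**Cost.** The SAP text needs no new data. One or two arm A events leave the restricted analysis. Irinotecan delays may introduce a small bias the other way, so the two analyses should be read together, with the observed intervals showing which is the more affected.

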	at 95%, estimated from randomization date to the date of death,
	whatever the cause, using the Kaplan-Meier method.
	Secondary endpoints: The accordary efficacy endpoint include:
	The secondary efficacy endpoint include:
	- Progression-free survival (PFS), defined as the time (days) from
	date of randomization to date of first observed disease
	progression (investigator's radiological or clinical assessment) or
	death due to any cause, if death occurs before progression is
	documented. Patients without tumor progression or death at the
	time of analysis will be censored at their last date of tumor
	assessment.
	- Time to Deterioration is defined as the time between the date of
	randomization and the first time the patient has a WHO ≥ 2 during
	treatment.
	- Disease control rate (DCR), defined as the rate of patients,
	whose best response was not progressive disease (i.e., CR, PR or
	SD), to all randomized patients in the treatment group
	- Objective response rate (OOR), defined as the rate of patients
	with CR or PR, to all randomized patients in the treatment group.
	Patients prematurely discontinuing without an assessment will be
	considered non-responders for the analysis.
	- Safety will be evaluated using the NCI-CTCAE version 5.0 scale;
	at each visit for the duration of the treatment.
	-Quality of life will be evaluated, using the EORTC QLQ-C30
	questionnaire.
	The expected benefit is an overall survival improvement of this
	treatment in patients with metastatic colorectal cancer who have
	received all standard treatments except TAS-102 and
	Regorafenib.

RISK AND BENEFITS	Toxicity and tolerance will be clinically and biologically assessed and rated on the NCIC CTCAE V5.0 scale at each visit. The expected benefit is an improvement in the overall survival of this treatment in patients with metastatic colorectal cancer who have received all standard treatments except TAS-102 and regorafenib. The risks of the study are continuously assessed by the MHI's pharmacovigilance department. This risk-benefit will be discussed in periodic safety reports. These reports will include all regulatory aspects and will be submitted to the competent authorities.
ELIGIBILITY CRITERIA	
	Signed informed consent obtained before any study specific procedures
	2. Male or female ≥ 18 years of age
	Histological documentation of adenocarcinoma of the colon or rectum
	Patients with metastatic colorectal cancer

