4.2 Inclusion criteria

- 1. Signed informed consent obtained before any study specific procedures
- 2. Male or female ≥ 18 years of age
- 3. Histological documentation of adenocarcinoma of the colon or rectum
- 4. Patients with metastatic colorectal cancer
- 5. Progression during or within 3 months following the last administration of approved standard therapies, which must include a fluoropyrimidine (or raltitrexed), oxaliplatin, irinotecan, anti-VEGF therapy and an anti-EGFR therapy (for RAS wild-type tumors), encorafenib
- 6. ECOG performance status ≤1
- 7. Life expectancy of at least 3 months
- 8. Patients with A/A CCND1 genotype of rs603965 CCND1
- 9. Adequate bone marrow, liver and renal function as assessed by the following laboratory requirements conducted within 7 days of starting study treatment:

- Lipasémie ≤1.5 x ULN
- Total bilirubin ≤ 1.5 x ULN
- Alanine aminotransferase (ALT) and aspartate aminotransferase (AST) ≤ 3.0 x
 ULN (≤ 5 x ULN for patients with liver involvement of their cancer)
- Alkaline phosphatase (ALP) ≤ 2.5 x ULN (≤ 5.0 x ULN for patients with liver involvement for their cancer and/or have bone metastases)
- Platelet count ≥ 100,000/mm3; Hemoglobin (Hb) ≥ 9 g/dL; Absolute neutrophil count (ANC) ≥ 1,500/ mm3. Transfusion to meet the inclusion criterion will not be allowed
- Serum creatinine ≤ 1.5 x ULN
- 10. International normalized ratio (INR) \leq 1.5 x ULN and partial thromboplastin time (PTT) or activated partial thromboplastin time (aPTT) \leq 1.5 x ULN unless receiving treatment with therapeutic anticoagulation. Patients being treated with anticoagulant, e.g., heparin, will be allowed to participate provided no prior evidence of an underlying abnormality in these parameters exists. Close monitoring of at least weekly evaluations will be performed until INR and PTT are stable based on a predose measurement as defined by the local standard of care
- 11. Women of childbearing potential must have a blood or urine pregnancy test performed a maximum of 7 days before start of study treatment, and a negative result must be documented before start of study treatment

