Appendix 5) must be performed if only it weren't performed at the end of

treatment visit.

(CT scan of the abdomen, pelvis and chest or hepatic MRI and CT scan of the

pelvis and chest without injection).

Tumor markers: CEA (Carcino-Embryogenic Antigen), CA 19.9 (Carbohydrate

Antigen 19-9) if not done at the EOT visit

Concomitant medications (including anti-cancer medication)

Adverse events documentation

Follow-up every other month until Death

Vital status

Anti-cancer medications

Telephone follow-up is acceptable. Site staff must use caution when contacting the patient's family for this information, especially if they are no longer under the care of the investigator,

so as to not inadvertently cause any distress to the family of a patient who is no longer alive.

6. Treatments

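### Time to Deterioration omits a performance-status decline first seen after treatment stops, and death, and has no censoring rule or analysis

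*Combined protocol and SAP*

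**What the plan says.** **Definition.** Section 2.2.2 ends Time to Deterioration at "the first time the patient has a WHO \geq 2 during treatment". The synopsis has the same rule ("randomization and the first time the patient has a WHO ≥ 2 during" treatment). Neither mentions death or censoring.

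**PFS, one bullet earlier.** PFS counts "death due to any cause, if death occurs before progression is documented", and it has a censoring rule: "Patients without tumor progression or death at the time of analysis will be censored at their last date of tumor assessment".

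**Entry.** Eligibility requires "ECOG performance status ≤1" (section 4.2), so an ECOG of 2 or more is a real worsening.

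**When ECOG is taken.** Section 5.3 lists it at day 1 and day 15 visits. It is next listed in section 5.4: "When a patient is taken off treatment, the following assessments should be performed within 14 days after study treatment has stopped", and only if the last evaluation is more than 7 days old. Note b to the table in section 5.1 adds a margin of 7 days either way.

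**Afterwards.** Section 5.5 lists no ECOG at the 30-day safety visit. Its heading "Follow-up every other month until Death" covers only survival status and later anticancer drugs.

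**Analysis.** Section 9.3 names tests for overall survival, PFS, response and disease control, and a time-to-event method for quality-of-life scores, but nothing for Time to Deterioration. It says that a separate SAP will follow before database lock.

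**The concern.** The endpoint is meant to show how long patients keep a good performance status. Treatment may be stopped for progression or because continuing would harm the patient (section 8.1), so stopping is plausibly linked to decline. The rule ends the capture of events at the point where some declines first become visible. The ECOG that would show them is taken after the last dose, and a patient who dies without an earlier on-treatment ECOG of 2 or more never has an event.

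If such patients are censored when treatment stops, the Kaplan-Meier and log-rank assumption of non-informative censoring fails. The endpoint would then look better than the truth in both arms. The comparison would also be distorted if the lost share differs between REGIRI and regorafenib alone. The trial is open-label, and the reasons for stopping need not match between arms.

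**Working it through.** **1. The plan's own figure.** None exists for Time to Deterioration: no event count, power or expected median is stated. The 55 events in section 9.1 concern overall survival and do not bear on this point.

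**2. Which outcomes count under the written rule**

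| What happens | Event as written? |
|---|---|
| ECOG ≥ 2 recorded at an on-treatment visit | Yes |
| ECOG 0–1 at the last on-treatment visit, ECOG ≥ 2 first recorded at the end-of-treatment visit | No, on a literal reading: the visit follows the stop |
| Death with no earlier on-treatment ECOG ≥ 2 | No: death is not named |
| Decline after the end-of-treatment visit | Cannot be seen: no ECOG is scheduled |

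The loss is therefore confined to declines first seen after the last on-treatment visit, and to deaths without a recorded on-treatment decline.

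**3. Effect if the lost cases are censored.** Censoring at the stop is an assumption, because the documents give no rule. Let q be the share of first deteriorations (ECOG ≥ 2 or death) that the rule does not count. Assume a constant hazard λ, independent exits for other reasons, and censoring of the lost cases when they occur. Then:

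- recorded hazard = (1−q) × λ
- recorded median = true median ÷ (1−q)

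With an assumed true median of 3 months:

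| q (assumed) | Recorded median, months |
|---|---|
| 0 | 3.0 |
| 25% | 3/0.75 = 4.0 |
| 50% | 3/0.50 = 6.0 |
| 75% | 3/0.25 = 12.0 |

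A simulation under the same assumptions, with other exits at a median of 3 months, gave 3.0, 4.0, 6.0 and 12.2.

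**4. Effect on the comparison.** With no true difference, the apparent hazard ratio (REGIRI versus regorafenib) is (1−qA)/(1−qB), where A is REGIRI and B is regorafenib alone:

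- equal q: 1.0
- qA = 25%, qB = 50%: 0.75/0.50 = 1.5
- qA = 50%, qB = 25%: 0.50/0.75 = 0.67

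The last two fall on opposite sides of 1. The arithmetic shows that bias is possible but does not show which way it goes.

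**5. Can equal q be taken for granted?** Two places suggest not.

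- Section 6.3 handles grade 4 non-haematological toxicity differently by arm: permanent stop in Table 6 (REGIRI), delay and reduction with optional stop in Table 10 (regorafenib alone). This is cited only as a reason why stopping may differ.
- The opening list in section 5.3 puts ECOG on day 15 for both arms, while the schedule table and the later day-15 lists give it for REGIRI only. Fewer on-treatment assessments would leave more declines to be first seen after stopping. These passages must be reconciled.

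**The case against.** **Handling is undefined, not wrong.** There is no censoring rule and no named analysis, and the SAP could still treat death as an event or a competing risk. A reader might infer that patients who stop or die because they declined are recorded as never having deteriorated. The documents do not say that; they say only what the event is. This part of the objection stands. The SAP cannot fully repair the point, though, because the event definition sits in the protocol and limits the event to the treatment period.

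**The end-of-treatment ECOG is not expressly excluded.** True: the exclusion follows from the plain meaning of the definition together with the timing of the visit. If that ECOG was meant to count, the text should say so.

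**Most declines may be caught.** With visits on day 1 and day 15, many patients will be seen at ECOG 2 or more before stopping, and these count. The documents give no share either way, and section 8.1 does not list performance status by name as a reason to stop. It would be too strong to say that the endpoint misses the most serious deteriorations in general.

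**Leaving out death is a design choice.** Overall survival and PFS already capture it, and q above treats death as part of deterioration. That is fair. But if death stays outside the endpoint it is a competing event, and the plan must still say how it is handled.

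**Conclusion.** The definition needs correcting. As written it leaves out two outcome-related groups: declines first recorded after the last on-treatment visit, and deaths without an earlier on-treatment ECOG of 2 or more. This is a stated rule that loses events, not only a missing detail.

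The consequence is conditional. If those patients are censored at stopping, time to deterioration is overestimated in any arm where q exceeds zero. If q differs between arms, the comparison is biased in a direction that the documents do not settle. A reader might infer that the rule favours REGIRI, or whichever arm stops more patients at the moment of decline. No figure in the documents supports a direction or a size. The medians of 4.0 and 6.0 months and the hazard ratios of 0.67 and 1.5 rest wholly on assumed values of q, a constant hazard and an assumed 3-month median.

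This is a secondary endpoint with no planned power. The primary overall survival analysis is unaffected.

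**What to change.** **In section 2.2.2 and the synopsis**

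- Remove the restriction to the treatment period.
- Define the event as the earlier of (a) the first ECOG ≥ 2 at any assessment up to and including the end-of-treatment visit, and (b) death from any cause within one stated window after the last ECOG, for example one two-month follow-up interval.
- Censor all other patients at their last ECOG assessment.

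**In section 9.3 and the SAP**

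- Name the analysis: Kaplan-Meier estimates and the RAS-stratified log-rank test already specified for PFS, in the ITT population.
- Add a sensitivity analysis of ECOG ≥ 2 with death as a competing risk.
- Report by arm how many events come from on-treatment visits, the end-of-treatment visit and death, so that the share affected is visible.
- Fix these choices before any outcome data are examined by arm, since the trial is open-label.

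**Cost.** A few sentences. Survival status is already followed until death, and the end-of-treatment ECOG is already scheduled, so no visit is added. The endpoint becomes a composite with death, and reported times will be shorter.

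**What remains.** The end-of-treatment ECOG may be skipped when the last evaluation is 7 days old or less. A decline after that visit, followed by a death beyond the window, stays unobserved. Some informative censoring will therefore persist and should be acknowledged in the report.
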